; BSTK: bedside sensory testing kit; C-SSRS: Columbia Suicide Severity Rating Scale; DSIS: Daily Sleep Interference Scale; e-diary: electronic diary; ETT: early termination of treatment; HbA1c: hemoglobin A1c (glycosylated hemoglobin); ICF: informed consent form; LIP: licensed independent practitioner; Nf-L: neurofilament light chain; NPRS: numeric pain rating scale; PE: physical examination; PGIC: patient global impression of change; q12h: every 12 hours; qd: once daily; tid: 3 times per day

- At each visit, documentation of the previous day's NPRS score by the subject should be confirmed before performing any assessments. When assessment time points coincide, assessments will be performed in the following order: patient-reported outcomes (e.g., NPSI), vital signs, 12-lead ECG, PE, and blood sample collection.
- On Day 1 and the Week 5 visit, all assessments must be completed before the first daily dose of study drug, except for the postdose PK and ECG sampling.
- If a subject prematurely discontinues study treatment, an ETT Visit should be scheduled as soon as possible after the subject decides to terminate study treatment; the subject will be encouraged to complete the capsule (pregabalin reference or matched placebo) study drug taper. Subjects who prematurely discontinue treatment will be encouraged to stay in the study, including completing the daily diaries and returning for clinical visits to complete study efficacy assessments (i.e., NPRS, PGIC, DSIS, NPSI, use of rescue medication, and SF-MPQ-2). These subjects will also be required to complete the Safety Follow-up Visit. If the ETT Visit occurs 14 days or later following the last tablet of study drug, then the ETT Visit will replace the Safety Follow-up Visit, and a separate Visit will not be required.
- d After the Treatment Period (capsule dosing tid), subjects will taper off capsule (pregabalin reference or matched placebo) study drug as follows: 4 days of dosing q12h, then 3 days of dosing qd in the evening.
- e Results from the Day 1 urine pregnancy, drug, and alcohol tests are required before the first dose.
- f Pregnancy tests will only be performed for female subjects of childbearing potential.

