9 STUDY IMPLEMENTATION

9.1 Study Design

This is a Phase 2, randomized, double-blind, active-controlled, dose-ranging, 4-arm, parallel-design study. Subjects who meet eligibility criteria during Screening Visits 1 and 2 will enter a 7-day Run-in Period to establish their baseline NPRS pain score. Subjects with a baseline average NPRS score of ≥4 points with limited variation (SD <25% of mean) will be eligible for the 12-week Treatment Period followed by a Safety Follow-up Visit (Figure 9-1).

Figure 9-1 VX21-548-103 Study Design

N: number of subjects

^a At the end of the Treatment Period (Week 12), subjects will taper off capsule (pregabalin reference or matched placebo) study drug for 7 days.

A total of approximately 175 subjects will be randomized 2:2:1:2 to 4 treatment arms: VX-548 (high, mid, or low dose) or pregabalin (reference arm; Table 9-1). Randomization will be stratified by sex (female and male) and BMI (\geq 30 and \leq 30 kg/m²). To maintain the blind, all subjects will receive the same number of tablets once daily (qd) in the morning and the same number of capsules 3 times per day (tid) in a double-dummy design. After the Treatment Period, subjects will taper off capsule (pregabalin reference or matched placebo) study drug for 7 days (4 days of dosing every 12 hours, then 3 days of dosing qd), and the Safety Follow-up Visit will occur an additional 7 (\pm 2) days later.

Subjects will stop taking pain medications (including pregabalin, if applicable), except acetaminophen (500 mg), for at least 14 days before the first dose of study drug.

Acetaminophen will be permitted as a pain rescue medication as needed (prn) throughout the study. Subjects will be permitted to take 500 mg every 4 to 6 hours prn, up to a maximum of 2500 mg in any 24-hour period. Subjects will record rescue medication use, and their current pain score on the NPRS immediately before each administration of rescue medication.

Table 9-1 VX21-548-103 Treatment Arms

| Treatment | Active Dose | Number of Subjects |
|--------------------|-------------|--------------------|
| VX-548 (high dose) | 69 mg qd | 50 |
| VX-548 (mid dose) | 46 mg qd | 50 |
| VX-548 (low dose) | 23 mg qd | 25 |
| Pregabalin | 100 mg tid | 50 |

qd: once daily; tid: 3 times per day

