9.1.4 Early Termination of Treatment

If a subject prematurely discontinues study treatment, an Early Termination of Treatment (ETT) Visit should be scheduled as soon as possible after the subject decides to terminate study treatment; the subject will be encouraged to complete the capsule (pregabalin reference or matched placebo) study drug taper.

Subjects who prematurely discontinue treatment will be encouraged to stay in the study, including completing the daily diaries and returning for clinical visits to complete study efficacy assessments (i.e., NPRS, PGIC, DSIS, use of rescue medication, b. These subjects will also be required to complete the Safety Follow-up Visit, approximately $14 (\pm 2)$ days after their last tablet dose of study drug. The assessments performed at the Safety Follow-up Visit are listed in Table 3-2.

If the ETT Visit occurs 14 days or later following the last tablet dose of study drug, then the ETT Visit will replace the Safety Follow-up Visit, and a separate Safety Follow-up Visit will not be required. If the ETT Visit is within a week of any scheduled visit in the Treatment Period, it will replace that scheduled visit, and a separate visit will not be required.

If a subject withdraws consent for the study, no further assessments will be performed. Vertex may retain and continue using the study data and samples after the study ends, and may use the samples and information in the development of the study compound, for other drugs and diagnostics, in publications and presentations, and for educational purposes. If a subject withdraws from the study, the study data and samples collected will remain part of the study (Section 9.10).

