9.4 Study Restrictions

Study restrictions are summarized in Table 9-2. A non-exhaustive list of study restrictions will be provided in the Study Reference Manual.

Table 9-2 Study Restrictions

| Restricted | Timing of Restriction | | |
|---|--|--|--|
| Medication/Food/Activity a | Start | Stop | |
| Other investigational drugs or devices | 30 days before first dose of study drug, 5 half-lives before first dose of study drug, or time determined by local requirements (whichever is longer) | Completion of SFU assessments | |
| Any opioid use for chronic (including neuropathic) pain; for acute use, refer to Section 8.2 and Section 11.5.2 | 3 months before Screening Visit 1 | Completion of Week 12 or ETT Visit assessments | |
| Marijuana or marijuana products | 14 days before first dose of study drug | Completion of Week 12 or ETT Visit assessments | |
| Pregabalin (except use of reference study drug) and gabapentin | 14 days before first dose of study drug | Completion of study drug taper (i.e., 7 days after Week 12 or ETT Visit) | |
| Capsaicin patch | 90 days before first dose of study drug | Completion of Week 12 or ETT Visit assessments | |
| Lamotrigine, carbamazepine, oxcarbazepine, phenytoin, topiramate, valproic acid, mexiletine, and topical agents being prescribed for pain control | 14 days before first dose of study drug | Completion of Week 12 or ETT Visit assessments | |

Table 9-2 Study Restrictions

| Restricted | Timing of Restriction | | |
|--|--|---|--|
| Medication/Food/Activity a | Start | Stop | |
| All SNRIs and tricyclic antidepressants | 14 days before first dose of study drug | Completion of Week 12 or ETT Visit assessments | |
| All other treatments for pain, except acetaminophen (500 mg) and study drug (as outlined in Section 9.4.1), including nonpharmaceutical interventions | 14 days before first dose of study drug | Completion of Week 12 or ETT Visit assessments | |
| Oral steroids | 5 half-lives or 2 days (whichever is longer) before first dose of study drug | Until last dose of study drug is taken | |
| Medications, herbal and dietary supplements (including St. John's wort) known to be moderate or strong inducers of CYP3A | 14 days before first dose of study drug | Completion of SFU assessments | |
| Proton Pump Inhibitors | 72 hours before first dose of study drug | Until last dose of study drug is taken | |
| H2 blockers | 12 hours before each morning dose of study drug | 6 hours after each morning dose of study drug | |

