- If a subject forgets the morning dose (tablets and capsule), and more than 2 hours have elapsed, they are to skip that capsule dose and resume at the next scheduled dose, but should take the tablets with the midday capsule dose. If a subject continues to forget the tablet dose and more than 2 hours have passed since the scheduled midday capsule dose, the subject should skip that tablet dose and resume at the next scheduled tablet dose (i.e., the next day).
- A capsule should not be taken within 4 hours of the last capsule, and 2 capsules should not be
 taken together. Therefore, assuming a schedule of every 6 hours during waking hours, if a
 subject forgets the midday dose (capsule), and more than 2 hours have elapsed, they are to
 skip that capsule dose and resume at the next scheduled dose.

Last Dose

The last dose of tablet study drug will be taken on the morning of the Week 12 Visit according to the subject's daily schedule, along with the morning dose of capsule study drug for that day. The midday and evening doses of capsule study drug will be taken as usual that day.

Taper

The taper regimen for the capsule study drug will begin the day after the Week 12 Visit. Dosing for this 7-day taper is as follows: 1 capsule in the morning and 1 capsule in the evening for 4 days, followed by 1 capsule in the evening for 3 days; the taper is then complete.

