# **9 STATISTICAL ANALYSIS**

## **9.1 General Considerations**

The Schedule of Assessments is provided in Section 3 of the CSP. The precision standards for reporting variables are provided in an internal Biometrics document that specifies the programming rules including the precision for derived variables.

All individual subject data for subjects who were randomized or received at least 1 dose of study drug will be presented in individual subject data listings.

**Continuous variables** will be summarized using the following descriptive summary statistics: the number of subjects (n), mean, standard deviation (SD), median, minimum value (min), and maximum value (max), unless otherwise specified.

**Categorical variables** will be summarized using counts and percentages.

**Baseline value:** The baseline for the weekly average of NPRS and DSIS will be defined as average of the non-missing scores from Day -7 to Day -1. For the weekly average of NPRS, baseline values will be calculated if there are at least 4 non-missing scores. For weekly average of DSIS, baseline values will be calculated if there are at least 3 non-missing scores. For ECGs, the baseline values will be defined as the most recent average of non-missing triplicate measurements collected before the first dose of the study drug. For all other variables, baseline values will be defined as the most recent non-missing measurement collected before the first dose of study drug, unless otherwise specified.

**Change (absolute change) from baseline** will be calculated as post-baseline value – baseline value.

**Treatment-emergent (TE) Period** will include the time period from the date of the first dose of study drug to either (1) the Safety Follow-up Visit, (2) the ETT Visit if it replaces the Safety Follow-up Visit, or (3) 14 days after the last dose for subjects who do not have a Safety Follow-up Visit or equivalent.

**Unscheduled visits:** Unscheduled visit measurements will be included in the analysis as follows:

- In scheduled visit windows per specified visit windowing rules
- In the derivation of baseline
- In the derivation of maximum and minimum values during the TE period, and maximum and minimum change from baseline values during the TE period for safety analyses
- In individual subject data listings as appropriate

**Visit windowing rules:** The analysis visit windows for protocol-defined visits are provided in [Appendix A](#).

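### After early termination, the capsule taper is dated from the ETT Visit and the final safety visit from the last tablet, so a late ETT Visit can leave blinded capsule dosing outside adverse event collection and the treatment-emergent period

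*Protocol*

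**What the plan says.** **Completers.** Tablets stop at the Week 12 Visit, and "The taper regimen for the capsule study drug will begin the day after the Week 12 Visit" (Protocol 9.6). The taper is "4 days of dosing q12h, then 3 days of dosing qd in the evening" (Protocol Table 3-2, footnote d). After it, "the Safety Follow-up Visit will occur an additional 7" (± 2) days later (Protocol 9.1). Section 9.1.3 gives the same visit as 14 ± 2 days after the end of the Treatment Period.

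**Early terminators.**
- The ETT Visit "should be scheduled as soon as possible after the subject decides to terminate study treatment" (Protocol 9.1.4). No maximum interval from the last tablet is given.
- At that point "the subject will be encouraged to complete the capsule (pregabalin reference or matched placebo) study drug taper" (Protocol 9.1.4).
- Only Table 9-2 dates this taper. Its pregabalin and gabapentin row ends the restriction at "Completion of study drug taper (i.e., 7 days after Week 12 or ETT Visit".
- Safety Follow-up is about 14 (± 2) days after the last tablet. "If the ETT Visit occurs 14 days or later following the last tablet dose of study drug", the ETT Visit takes its place (Protocol 9.1.4; Table 3-2, footnote c, has the same replacement rule).

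**Treatment-emergent (TE) period** (Protocol 12.3.1, SAP 9.1). There are three alternative ends: rule 1, the Safety Follow-up Visit; rule 2, given in the SAP as "2) the ETT Visit if it replaces the Safety Follow-up Visit"; and rule 3, 14 days after the last dose for subjects with neither visit. Rule 3 does not say whether the dose is tablet or capsule.

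**Adverse event (AE) collection** (Protocol 13.1.1.3). It runs through Safety Follow-up. Without that visit, it ends at the earlier of 14 days after the last tablet and an ETT Visit held 14 or more days after the last tablet. After Safety Follow-up, only SAEs considered related are still reported (Protocol 13.1.2.2).

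**The concern.** For completers, the last tablet and the start of the taper clock fall on the same visit, so the schedule leaves a capsule-free interval before the final safety assessment. After early termination the two clocks start at different events. Each day between the last tablet and the ETT Visit moves the end of the taper later but leaves Safety Follow-up where it was.

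If the ETT Visit is late enough, a subject following the rules as written is still taking blinded capsules at, or after, the visit that closes both AE collection and the TE period. A non-serious event, or an SAE not considered related, that starts in the remaining taper is then outside AE collection. The SAP counts an event as treatment-emergent only if it starts or worsens before the TE period ends, so it would not be tabulated either. When the ETT Visit replaces Safety Follow-up, the C-SSRS that Table 3-2 schedules at Safety Follow-up is lost as well.

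Safety and tolerability is a primary objective. Capsules are active only in the pregabalin arm (Table 9-3), so events on active drug could be missed only in the reference arm.

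**Working it through.** **Inputs.** Taper: 4 days at two capsules plus 3 days at one (Table 3-2, footnote d). Taper end: 7 days after the ETT Visit (Table 9-2). Safety Follow-up (SFU): Day 12 to 16 after the last tablet, or the ETT Visit itself from Day 14 (9.1.4). Day 0 is the last tablet, and E is the number of days from it to the ETT Visit. E is not given, so it is varied. As for completers, the taper is assumed to start the day after the visit.

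**Completers' schedule reproduced.** Taper = 4 + 3 = 7 days. SFU = 7 + 7 (± 2) = Day 14 (12 to 16), which matches 9.1.3. Capsule-free interval = (12 to 16) − 7 = 5 to 9 days.

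**Early terminators.** Taper days are E+1 to E+7, so the last capsule is on Day E+7. Gap = SFU day − (E + 7). A zero or negative gap means that the last capsule is on or after the visit.

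| E | Last capsule | Gap, SFU Day 12 / 14 / 16 | Taper days on or after SFU |
|---|---|---|---|
| 0 | Day 7 | 5 / 7 / 9 | 0 / 0 / 0 |
| 4 | Day 11 | 1 / 3 / 5 | 0 / 0 / 0 |
| 5 | Day 12 | 0 / 2 / 4 | 1 / 0 / 0 |
| 7 | Day 14 | −2 / 0 / 2 | 3 / 1 / 0 |
| 9 | Day 16 | −4 / −2 / 0 | 5 / 3 / 1 |
| 10 | Day 17 | −5 / −3 / −1 | 6 / 4 / 2 |
| 14 or more | Day E+7 | ETT Visit is the final visit; gap −7 | all 7 |

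E = 0 gives the completers' interval. There is no overlap through E = 4. Overlap is possible from E = 5, occurs at the nominal Day 14 visit from E = 7, and is certain from E = 9. From E = 14 the whole taper, 4×2 + 3×1 = 11 capsules, follows the final safety visit.

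**AE collection without an SFU Visit.** It ends on Day 14, and 14 − (E + 7) gives its position relative to the last capsule: 7 days after it at E = 0, the same day at E = 7, and 7 days before it at E = 14.

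**TE rule 3.** It ends on Day 14 if the last dose means the tablet, or on Day E + 7 + 14 = E + 21 if it means any study drug. At E = 7 that is Day 14 or Day 28. On the second reading the TE period runs on after AE collection has stopped.

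**Other reading of the taper start.** If the taper instead began the day after the last tablet, it would end on Day 7. SFU would then leave 5 to 9 capsule-free days, and a replacing ETT Visit at least 14 − 7 = 7. The overlap therefore depends on the Table 9-2 date.

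**The case against.** The strongest reply is that the taper date is inferred. Table 9-2 is a medication-restriction table, Section 9.6 dates a taper only after the Week 12 Visit, and 9.1.4 encourages a taper without dating it. If the taper starts when regular dosing stops, there is no overlap at any E. But that reading contradicts Table 9-2, the only text that dates the taper after early termination. The documents also do not say whether capsules continue between the last tablet and the ETT Visit. This is a reason to reconcile the passages, not a reason to find them consistent.

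The second reply is that the sequence is conditional: the ETT Visit should be prompt, and the taper is optional. That stands, and it limits the size. Yet the protocol itself provides for an ETT Visit at 14 days or later and makes no exception to the taper for it.

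Four stronger readings are tempting, and the documents do not support them.
- **That the TE period runs from the last tablet.** No rule says so. Rules 1 and 2 depend on the tablet only through the visit that closes them, and rule 3 names no drug. The explicit tablet clock is in AE collection.
- **That the lost events are seen by no visit.** Early terminators remain in the study (9.1.2), are encouraged to keep attending (9.1.4), and are asked about AEs at each visit (13.1.1.3). The formal collection window has closed, but contact need not have ended.
- **That the safety comparison with pregabalin is biased.** Safety is descriptive, without testing, and its objective concerns VX-548. Capsules taken after Safety Follow-up are placebo in the VX-548 arms. Missed events would tend to understate pregabalin AEs, but by an amount that cannot be derived.
- **That a quarter of subjects are affected.** The 25% is the dropout allowance in the sample-size section. It does not count late ETT Visits.

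**Conclusion.** The point holds, conditionally. Following the stated rules, a subject with a late ETT Visit who takes the taper as Table 9-2 dates it can be on blinded capsules when AE collection and the TE period close. Prompt ETT Visits (E of 4 or less) give no overlap, although E of 1 to 4 shortens the capsule-free interval.

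The number affected is not stated and is probably small, since it needs both a late visit and an optional taper. If discontinuation runs at the planned 25% and every dropout is an early terminator, the ceiling is 0.25 × 50 = 12.5 pregabalin subjects and 0.25 × 175 = 43.75 overall. Only those with a late ETT Visit who take capsules after it would count.

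The result rests on the Table 9-2 taper date, on a taper starting the day after the ETT Visit, and on an unknown E. The primary efficacy analysis is untouched. It is still more than missing detail, because the rules can class an event during study-drug dosing as not treatment-emergent. It should be corrected.

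**What to change.** 1. Reconcile Protocol 9.1.4, Table 3-2 (footnotes c and d), Table 9-2, 12.3.1 and 13.1.1.3 with SAP 9.1, so that the taper, final safety visit, AE collection and TE period are consistent after early termination. Whether and when a taper follows a late ETT Visit, and when the final visit is held, are for the sponsor to decide.
2. In the TE definition (Protocol 12.3.1 and SAP 9.1), state that the last dose in rule 3 means any study drug, tablet or capsule, and that rules 1 and 2 do not close the TE period before the last dose of any study drug.
3. Match AE collection in Protocol 13.1.1.3 to this. Without that, a longer TE period would contain no newly collected non-serious events.

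Items 2 and 3 cover events up to the last capsule. Cover after it depends on what the sponsor decides under item 1.

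The cost is wording changes in the protocol, one sentence in the SAP, and slightly longer AE collection for a few subjects.

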9.1.5 Home Health Visits

Home health visits are only an option if permitted by local regulations. Any visits that occur via home health must have a consultation (i.e., telemedicine video conference or telephone contact) between the subject and investigator or qualified delegate (licensed independent practitioner [LIP]) within 2 business days after the home health visit in order to check-in and collect AEs, and may also include a separate follow up with the study coordinator.

9.2 Method of Assigning Subjects to Treatment Groups

An interactive web or voice response system (IXRS) will be used to assign subjects to treatment. The randomization code will be produced by Vertex Biostatistics or a qualified randomization vendor. The Vertex study biostatistician will review and approve the production of the final randomization list, which will be reviewed and approved by a designated unblinded biostatistician who is not a member of the Study Execution Team (SET).

9.3 Rationale for Study Elements

9.3.1 Study Design

This study is designed to evaluate the efficacy of VX-548 for treatment of pain in subjects with painful DPN. The randomized, double-blind study design will limit observer bias and reduce the possibility for unblinding. For the primary endpoint, daily NPRS pain scores will be averaged over a weekly period to reduce the impact on the analyses of individual high or low pain scores.

9.3.2 Study Drug Dose

VX-548 doses (Table 9-1) were selected based on favorable safety and PK data from healthy volunteers in Study 001 (single ascending dose study) and Study 002 (multiple ascending dose study). Multiple oral doses up to 65 mg administered in solution/suspension under fasted conditions every 24 hours for 14 days have been evaluated and found to be safe and well tolerated. The selected VX-548 doses are predicted to achieve concentrations that are able to produce 80% (low dose) to 90% (high dose) Na_V1.8 inhibition in the in vitro human dorsal root ganglia assay.

Based on observed data, the mean exposures ($AUC_{0.24}$ and C_{max}) for VX-548 and its major metabolite, M6-548, at the highest dose in this study (69 mg qd without regard to food administered as tablets) are predicted to provide the following safety margins to the no-observed-adverse-effect level (NOAEL) observed in monkey in the 13-week GLP toxicity study:²²

- VX-548: 2.8-fold and 4.5-fold below the NOAEL for AUC₀₋₂₄ and C_{max}, respectively
- M6-548: 2.8-fold and 5.9-fold below the NOAEL for AUC₀₋₂₄ and C_{max}, respectively

The safety margins were calculated using observed PK data for the suspension/solution formulation of VX-548 and adjusted based on the relative bioavailability between the tablet and solution formulations of VX-548 and relative bioavailability between fasted conditions and fed conditions with high-fat meal for the tablet formulation.

